Table 8.43: Guidelines for Management of Toxicities That Occur during Maintenance Treatment				
Event	Action to Be Taken			
Hematologic toxicity: Grade 3 or 4	 Withhold rituximab and hyaluronidase human and venetoclax Administer G-CSF for neutropenia per institutional guidelines. Administer RBCs or platelets as required. If improvement to Grade 2, resume rituximab and hyaluronidase human at full dose and resume venetoclax next lower dose (Refer to table 8.21 for dose reduction steps.) Patients who are not eligible for further venetoclax dose reductions should be permanently discontinued. If study treatment is withheld for 21 days, permanently discontinue study treatment. 			
Non-hematologic toxicity: Grade 2	Withhold rituximab and hyaluronidase human and venetoclax If improvement to Grade ≤ 1 or baseline, resume rituximab and hyaluronidase human at full dose and resume venetoclax at next lower dose (Refer to table 8.21 for dose reduction steps). o a for subsequent cycles per guidelines o Patients who are not eligible for further venetoclax dose reductions should be permanently discontinued. • If study treatment is withheld for 21 days, permanently discontinue study treatment.			
Infections and Infestations: Hepatitis Viral	Discontinue therapy and treat hepatitis			

G-CSF granulocyte colony-stimulating factor.

Table 8.44: Prophylaxis and Assessments for Tumor Lysis Syndrome

1 4010 0.77. 1 1	Table 8.44: Prophylaxis and Assessments for Tumor Lysis Syndrome				
	High Risk	Regular Risk			
Definition	 Bulky disease defined as: Any lymph node ≥ 10 cm on the screening CT scan Circulating lymphoma cells Other characteristics deemed by the investigator to confer high risk of TLS 	All other patients not meeting definition of high risk			
Hospitalization	initial dose of venetoclax (See Hospitalization section below)	Not required, but may be hospitalized per discussion with the investigator and Medical Monitor			
Assessments	On the day of the initial visit with administration of venetoclax (Cycle 1, Day 1): Serial vital signs will be recorded • Patients who demonstrate electrolyte changes suggestive of TLS should undergo aggressive management and further monitoring as per standard of care and outlined in Appendix II. • Patients still at risk of TLS before the subsequent dose should receive adequate prophylaxis and monitoring.				

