LDH=lactate dehydrogenase; TLS=tumor lysis syndrome Obinutuzumab, rituximab, polatuzumab vedotin, and venetoclax-F. Hoffman-La Roche Ltd Protocol GO29833, Version 4

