TLS is a risk for patients with CLL who are treated with high cell-killing agents like venetoclax. Clinical data from patients with CLL treated to date with venetoclax suggest that patients with baseline lymph nodes ≥ 5 cm diameter are at a greater risk for TLS than those with baseline lymph nodes < 5 cm. In addition, the data showed that CrCl of ≤ 80 mL/min at screening was a secondary risk factor for TLS. A detailed description of risk factors for developing TLS following treatment with venetoclax is available in the venetoclax Investigator's Brochure.

Based on the data review performed by the Sponsors, the following three risk categories for developing TLS after treatment with venetoclax were defined (see Table 8). These risk groups were developed using assessments of nodal disease burden obtained from imaging tests performed at screening in several other studies of venetoclax in CLL. Therefore, assigning a patient's TLS risk MUST be made based on an imaging test performed at screening. Assessments of TLS risk categorization and monitoring/prophylaxis guidance is being continuously assessed throughout the venetoclax program, and future updates to these guidelines are possible.

TLS Risk Category

All measurable lymph nodes with the largest diameter < 5 cm and $< 25 \times 10^9$ /L ALC. Lymph node size will be determined by radiologic assessment.

Medium

Any measurable lymph node with the largest diameter ≥ 5 cm but < 10 cm OR $\ge 25 \times 10^9$ /L ALC. Lymph node size will be determined by radiologic assessment.

Any measurable lymph node with the largest diameter ≥ 10 cm or the presence of both $\ge 25 \times 10^9$ /L ALC AND any measurable lymph node with the largest diameter ≥ 5 cm but < 10 cm. Lymph node size will be determined by radiologic assessment.

Table 8 Risk Categories for Developing Tumor Lysis Syndrome

ALC=absolute lymphocyte count; CT=computed tomography; MRI=magnetic resonance imaging; TLS= tumor lysis syndrome.

TLS Risk Assessment MUST be made based on measurements of nodal disease burden based on radiologic assessments (CT scan or MRI) performed during the screening period.

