All patients enrolling in the study will be assessed at screening and categorized in a risk category as described above. Investigators may reassess patient's TLS risk after they start treatment and may assign them to a lower risk group. For example, patients classified as TLS high-risk at screening because of an ALC of $\geq 25 \times 10^9$ AND a measurable lymph node with the largest diameter ≥ 5 cm but < 10 cm by radiologic assessment may have a re-evaluation of their TLS risk category based on their most recent ALC after initiating study treatment. If the patient's ALC decreases to $< 25 \times 10^9$ /L, the patient may be categorized as TLS medium-risk and may follow the management guidelines for the TLS medium-risk category at subsequent visits and during the venetoclax ramp-up period. Re-assessment of the patient's TLS risk category can occur continuously during Cycle 1 and the venetoclax dose ramp-up period. If a patient is re-assigned to a lower risk group, the investigator may follow the prophylaxis guidance for the lower risk group to which they are assigned.

However, patients who are classified as high-risk because they have a lymph node with largest diameter ≥ 10 cm MAY NOT have their TLS risk re-assessed and should follow the prophylaxis plan for high-risk patients throughout the venetoclax ramp-up period.

Patients who develop signs or symptoms of TLS regardless of the risk group to which they were assigned may have additional monitoring at subsequent visits at the investigator's discretion.

This section describes the management of patients throughout dosing given their risk factors for developing TLS identified upon study entry.

Table 9 Summary of Tumor Lysis Syndrome Prophylaxis for venetoclax and Monitoring Measures

TLS Risk Category	Day 1 of Dose Level	Prophylaxis Medication	Hospitalization	Hydration ^a	Laboratory Assessments b, c

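### Table 8.44 makes circulating lymphoma cells alone a TLS High Risk criterion, while Appendix III can class the same patient Low Risk and outpatient for the first venetoclax dose; no visible text says which governs

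*Combined protocol and SAP*

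**What the plan says.** **Table 8.44** has two tiers. High Risk is any node of 10 cm or more, "Circulating lymphoma cells" with no count threshold, or other features that the investigator judges high risk. Everyone else is Regular Risk. The High Risk hospitalization cell, as far as it can be read, says "initial dose of venetoclax (See Hospitalization section below"; its opening words are lost. The Regular Risk cell says "Not required, but may be hospitalized per discussion with the investigator and Medical Monitor". The only appendix the table points to is Appendix II. The note beneath it names another study, "Protocol GO29833, Version 4".

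**Appendix III** has three tiers, built from "several other studies of venetoclax in CLL". The lowest begins "All measurable lymph nodes with the largest diameter < 5 cm" and also needs ALC below 25 x 10^9/L. Medium is a node of 5 to under 10 cm, or ALC of 25 or more. High is a node of 10 cm or more, or both Medium features together. Circulating lymphoma cells are not a criterion. Its scope is explicit: "All patients enrolling in the study will be assessed at screening and categorized in a risk category as described above". After treatment starts, investigators "may assign them to a lower risk group", except where a node is 10 cm or larger.

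For the initial 20 mg and 50 mg doses, Appendix III sends Low Risk patients, and Medium Risk patients with creatinine clearance (CrCl) of at least 80 mL/min, to outpatient dosing. Medium Risk patients with lower CrCl or higher tumor burden may be handled as high risk. High Risk patients are admitted.

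**The concern.** Both texts are in force, and they can give opposite answers for one patient on one question: is admission planned for the first venetoclax dose? Sections 3.1 and 3.2 set no ALC ceiling and do not exclude circulating disease, so such patients can enroll. Section 15.17 singles out CLL and MCL as settings where TLS on venetoclax is a particular risk, and section 7.711 counts grade 3 or higher TLS as a significant toxicity.

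Two sites could therefore manage the same patient differently, each following the protocol. The sources named in the two texts suggest that the schemes were brought in separately and not reconciled. The hospitalization section to which Table 8.44 points cannot be found in the visible text after the table.

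**Working it through.** No sample size, power or error rate is involved. The check applies both rule sets to the same patients and looks for a statement of precedence.

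**Inputs.** Table 8.44 definitions and hospitalization row; Appendix III Table 8 cut-offs (5 cm, 10 cm, 25 x 10^9/L) and its initial-dose text by tier. The label of the lowest tier in Table 8 is lost, but its place before Medium and the later Low Risk text identify it.

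**Step 1: patients with circulating lymphoma cells.** Three node bands x two ALC bands = 6 combinations.

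| Largest node | ALC (x 10^9/L) | Table 8.44 | Appendix III | Appendix III setting, initial doses |
|---|---|---|---|---|
| <5 cm | <25 | High | Low | Outpatient |
| <5 cm | ≥25 | High | Medium | Outpatient if CrCl ≥80; high-risk handling optional if CrCl <80 or higher tumor burden |
| 5 to <10 cm | <25 | High | Medium | As the row above |
| 5 to <10 cm | ≥25 | High | High | Admitted |
| ≥10 cm | <25 | High | High | Admitted |
| ≥10 cm | ≥25 | High | High | Admitted |

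The tiers agree in 3 of 6 and differ in 3 of 6 (two Medium, one Low). Splitting by CrCl (<80, ≥80 mL/min) doubles the grid to 12: 6 High, 4 Medium, 2 Low. The proportion is unchanged.

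**Step 2: an example with assumed values.** Circulating cells present, largest node 3 cm, ALC 10 x 10^9/L. Table 8.44: High Risk, with hospitalization tied to the first dose. Appendix III: 3 <5 and 10 <25, so Low Risk and outpatient for 20 mg and 50 mg.

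**Step 3: the reverse direction.** Without circulating cells, 1 of 6 combinations (node 5 to <10 cm with ALC ≥25) is High in Appendix III but Regular in Table 8.44, unless the investigator judges otherwise.

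**Step 4: what differs between the two texts.** Visible Table 8.44 gives High Risk patients the hospitalization entry, serial vital signs, and Appendix II management if electrolytes change. The demonstrated difference is therefore planned admission for the first dose. Three further measures belong to Appendix III's own High Risk tier: inpatient IV hydration of 2–3 L/day, a 12 h sample in addition to 8 h and 24 h, and rasburicase if pre-dose uric acid is high. They follow only if the patient is then managed in that tier.

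**Step 5: precedence.** Table 8.44 does not mention Appendix III. Appendix III does not mention Table 8.44. Footnote c to Appendix III Table 9 is permissive, and its marker is not on the low-risk row. Footnote 4 to the test schedule in section 4.0 relies on investigator judgment and does not choose between the schemes.

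**The case against.** The strongest reply has three parts.

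**The Table 8.44 evidence is damaged.** The verb in the High Risk hospitalization cell is missing, so a reader might infer that the table mandates admission. The documents do not show that. The contrast with the Regular Risk cell supports planned admission, but not how binding it is. Other rows or a precedence statement may also have been lost. This stands, and is why the point is limited to the visible text. The conflict in risk definitions does not depend on the missing words.

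**The loss is easily overstated.** A reader might infer that Table 8.44 promises IV hydration, a 12 h sample and rasburicase, all of which Appendix III takes away. It does not; see step 4. A reader might also infer that the outpatient is unprotected. Several safeguards say otherwise:

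- The first dose is given at the treatment center (section 7.2).
- The 8 h chemistry is reviewed before the patient leaves, and the 24 h results before the next dose. Extra laboratory tests are at the investigator's discretion (Appendix III, Low Risk).
- In every tier, clinically significant baseline abnormalities delay the first dose, with added prophylaxis if needed (Appendix III, initial doses).
- Patients meeting the Appendix II laboratory criteria within 24 hours should be hospitalized.
- If the investigator sees significant TLS risk in cycle 1, monitoring to the institution's standard is directed (section 4.0 footnote 4 and section 7.2).
- Section 15.17 credits the low starting dose and gradual ramp-up with lowering TLS risk, and this trial starts at 20 mg.

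These narrow the consequence considerably. They do not tell a site which scheme decides on admission.

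**Sites would choose the stricter rule.** They may, but no visible text says so, and Appendix III's outpatient instruction for Low Risk patients is directive.

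**Conclusion.** The conflict is real and narrow. For a patient with circulating lymphoma cells, all nodes under 5 cm and ALC below 25 x 10^9/L, Table 8.44 points to hospitalization around the first dose and Appendix III directs outpatient dosing. For the two Medium Risk combinations, Appendix III makes high-risk handling optional at most. No visible text ranks the schemes.

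This rests on two readings: that the damaged Table 8.44 cell plans admission, inferred from the cell opposite, and that no precedence statement was lost in extraction.

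The 3 of 6 figure counts rule combinations with equal weight. A reader might take it to mean that half of such patients are affected. The documents do not say how many patients will have circulating cells or how they spread over the combinations, so no frequency or risk follows. Sample size, power, decision rules and analysis are not affected. The point merits correction as an inconsistency in safety instructions.

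**What to change.** Add the same text to Table 8.44 and Appendix III:

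> A patient who is high risk for TLS under either Table 8.44 or Appendix III is managed under the Appendix III TLS High Risk procedures. Patients high risk under Appendix III are admitted for the 20 mg and 50 mg doses, as already stated. Patients high risk only under Table 8.44 are admitted at least for the 20 mg dose, and may be re-assessed before 50 mg unless a node is ≥10 cm.

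The two doses are named separately because a sentence limited to 20 mg could be read as dropping the 50 mg admission that Appendix III already requires. The last clause repeats Appendix III's bar on re-assessment; a node of that size is already high risk there.

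In the High Risk hospitalization cell of Table 8.44, replace the pointer to a section below with a reference to the Appendix III TLS High Risk text.

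The cost is one addition in two places and one corrected cross-reference. Sites that would have followed Appendix III will have some added first-dose admissions, with the High Risk measures that go with them. The number cannot be derived from the documents. Nothing in the statistical design changes.

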8.5 Management of Adverse Reactions for polatuzumab

Table 8.51 Management of Peripheral Neuropathy, Infusion-Related Reaction, and Myelosuppression

Table 8.51 Management of	Table 8.51 Management of Peripheral Neuropathy, Infusion-Related Reaction, and Myelosuppression				
Event	Dose Modification				
Grade 2–3 Peripheral Neuropathy	 Hold polatuzumab dosing until improvement to Grade 1 or lower. If recovered to Grade 1 or lower on or before Day 14, restart polatuzumab with the next cycle at a permanently reduced dose of 1.4 mg/kg. If a prior dose reduction to 1.4 mg/kg has occurred, discontinue polatuzumab. If not recovered to Grade 1 or lower on or before Day 14, discontinue polatuzumab. 				
Grade 4 Peripheral Neuropathy	Discontinue polatuzumab.				
Grade 1–3 Infusion- Related Reaction	 Interrupt polatuzumab infusion and give supportive treatment. For the first instance of Grade 3 wheezing, bronchospasm, or generalized urticaria, permanently discontinue polatuzumab. For recurrent Grade 2 wheezing or urticaria, or for recurrence of any Grade 3 symptoms, permanently discontinue polatuzumab. Otherwise, upon complete resolution of symptoms, infusion may be resumed at 50% of the rate achieved prior to interruption. In the absence of infusion related symptoms, the rate of infusion may be escalated in increments of 50 mg/hour every 30 minutes. For the next cycle, infuse polatuzumab over 90 minutes. If no infusion-related reaction occurs, subsequent infusions may be administered over 30 minutes. Administer premedication for all cycles. 				
Grade 4 Infusion- Related Reaction	 Stop polatuzumab infusion immediately. Give supportive treatment. Permanently discontinue polatuzumab. 				
Grade 3–4 Neutropenia ^{a,b}	 Hold all treatment until ANC recovers to greater than 1000/microliter. If ANC recovers to greater than 1000/microliter on or before Day 7, resume all treatment without any additional dose reductions. Consider granulocyte colony-stimulating factor prophylaxis for subsequent cycles, if not previously given. 				
Grade 3–4 Thrombocytopenia ^{a,b}	 Hold all treatment until platelets recover to greater than 75,000/microliter. If platelets recover to greater than 75,000/microliter on or before Day 7, resume all treatment without any additional dose reductions. 				
Infections and Infestations: Hepatitis Viral	Discontinue therapy and treat hepatitis				

^a Severity on Day 1 of any cycle.

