8.3 Toxicities during Induction Treatment

Table 8.31: Guidelines for Management of Hematologic Toxicities That Occur During Induction Treatment.

Heatment.					
Event	Action to Be Taken				
Grade 3 or	For patients who have had one or no prior venetoclax or polatuzumab vedotin				
4	dose reduction:				
Hematogic	• Withhold study treatment. ¹				
Toxicity ¹	 Administer RBCs or platelets as required. 				
	 If patient has not already initiated G-CSF, initiate prophylactic G-CSF for current and subsequent cycles. 				
	 Resume venetoclax and polatuzumab vedotin at same dose after interruption for 1st occurrence, once the toxicity has resolved to Grade 1 or baseline level 				
	 Resume venetoclax and polatuzumab vedotin at one level dose reduction after interruption for 2nd occurrence, once the toxicity has resolved to Grade 1 or baseline level. Refer to table 8.21 for dose reduction steps. 				
	• For patients who develop platelet count of 20,000/L while receiving LMWH, reduce the dose of LMWH. For patients who develop platelet count of 20,000/L while receiving platelet inhibitors, consider temporarily withholding platelet inhibitors.				
	No more than 2 dose level reductions in venetoclax and				
	polatuzumab vedotin are allowed during induction.				
	 Consider discontinuation of study drug for patients who require withholding study drug for more than 21 days. 				
	For patients who have had two prior venetoclax dose reductions:				
	 Permanently discontinue study treatment. 				
	 For grade 4 thrombocytopenia ≥ 7 days or grade 3 thrombocytopenia with ≥ grade 2 bleeding resume venetoclax and polatuzumab at one dose level dose reduction after the toxicity has resolved to Grade 1 or baseline level 				

(G-CSF) granulocyte colony-stimulating factor; (LMWH) low molecular weight heparin.

¹ Treatment delays apply to all toxicities; dose modifications apply only to toxicities that are considered to be related to any of the study treatment components. Toxicities that occur during the cycle and subside prior to the next cycle should not trigger the suggested dose modifications.

Table 8.32: Guidelines for Management of Non-Hematologic Toxicities That Occur During Induction

Table 8.32: Guide	elines for Management of Non-Hematologic Toxicities That Occur During Induction		
Event	Action to Be Taken		

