General guidance for treatment delays and discontinuation	 If study treatment is withheld for 21 days because of a toxicity that is attributable to study treatment, permanently discontinue study treatment. When a treatment cycle is delayed because of toxicity resulting from any component of the regimen, all study treatment should be held and resumed together to remain synchronized. 		
TLS	 Withhold study treatment.^a Correct electrolyte abnormalities, monitor renal function and fluid balance, and administer supportive care, including dialysis as indicated. If symptoms have resolved completely, resume rituximab and hyaluronidase human and polatuzumab at full dose and resume venetoclax at current dose. During venetoclax ramp-up, if venetoclax was withheld for 7 days or less, resume venetoclax at same dose level or at one lower dose level, as determined by the investigator (based on risk assessment, including tumor burden status). Refer to Table 8.21 for dose reduction steps. During venetoclax ramp-up, if venetoclax was withheld for more than 7 days, the dose must be resumed at one lower dose level, with the exception of the first dose (20 mg). Refer to Table 8.21 for dose reduction steps. If resolved within 24 to 48 hours of last dose, resume venetoclax at the same dose. For any blood chemistry changes requiring more than 48 hours to resolve, resume at a reduced dose. Refer to Table 8.21 for dose reduction steps. For any events of clinical TLS, resume at a reduced dose following resolution. Refer to Table 8.21 for dose reduction steps. 		
New-onset neurologic manifestations suggestive of PML AST, ALT, or bilirubin	 Withhold study treatment.^a Consult with a neurologist if PML is suspected. If PML is ruled out, resume rituximab and hyaluronidase human, polatuzumab vedotin and venetoclax at current dose. If PML is confirmed, permanently discontinue study treatment. 		
increase: Grade 3 (or 10x ULN for patients with liver involvement)	 If improvement to Grade 1, resume rituximab and polatuzumab vedotin at full dose and resume venetoclax at next lower dose for current and subsequent cycles per guidelines in Table 8.21. No more than 2 dose level reductions from original dose of venetoclax are allowed during induction. Patients who have had two prior dose reductions should be permanently discontinued. Refer to Table 8.21 for dose reduction steps. Permanently discontinue study treatment for life-threatening liver toxicity. 		

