Infections and Infestations; AE: Hepatitis viral	Discontinue therapy and treat hepatitis		

Table 8.32: Guidelines for Management of Non-Hematologic Toxicities That Occur During Induction (cont.)

Event	Grade	Action to Be Taken	
Peripheral Neuropathy	Grade 4	Permanently discontinue polatuzumab vedotin and all other study treatment.	
	Grade 2	1. Delay study treatment. a	
	or 3	2. If improvement to Grade 1 within 21 days, resume study treatment for current and subsequent cycles as follows:	
		a. Resume rituximab or rituximab and hyaluronidase human at full dose	
		b. Resume venetoclax at current dose ^a	
		c. For patients who started at 1.8 mg/kg, resume polatuzumab vedotin at the permanently reduced dose of 1.4 mg/kg;	
Other non-hematologic toxicities (i.e., not described above), excluding alopecia, nausea, and vomiting	Grade 3 or 4	 dose of 1.4 mg/kg; For patients who have had no prior dose reductions: Withhold study treatment.^a If improvement to Grade 1 or baseline, resume rituximab and polatuzumab vedotin at full dose and resume venetoclax at next lower dose ^a for current and subsequent cycles perguidelines. For patients who have had one prior dose reduction: Grade 4 events Permanently discontinue study treatment. Grade 3 events Withhold study treatment.^a If improvement to Grade 1 or baseline, rituximab and polatuzumab vedotin at full dose and resume venetoclax at next lower dose ^a for current and subsequent cycles per guidelines. No more than two dose level reductions from the original dose of venetoclax are allowed during induction. For patients who have had two prior dose reductions: Permanently discontinue study treatment. 	
	Grade 2	 Withhold study treatment.^a If improvement to Grade 1 or baseline, resume rituximab and polatuzumab vedotin, and venetoclax at full dose. 	

IRR-infusion-related reaction; PML-progressive multifocal leukoencephalopathy; TLS-tumor lysis syndrome; ULN-upper limit normal.

^a Treatment delays apply to all events; dose modifications apply only to events that are considered to be related to any of the study treatment components. Toxicities that occur during the cycle and subside prior to the next cycle should not trigger the suggested dose modifications.

8.4 Toxicities during Maintenance Treatment provides guidelines for management of toxicities that occur during maintenance treatment.

Table 8.43: Guidelines for Management of Toxicities That Occur during Maintenance Treatment

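### For Grade 2-3 neuropathy, Table 8.32 resumes polatuzumab after recovery within 21 days, Table 8.51 stops it after Day 14, and neither limit has a stated start

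*Combined protocol and SAP*

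**What the plan says.** **Neuropathy, Table 8.32 (section 8.3).** For Grade 2 or 3 peripheral neuropathy, study treatment is delayed. Then: "If improvement to Grade 1 within 21 days, resume study treatment for current and subsequent cycles as follows". The polatuzumab item of that list reads "For patients who started at 1.8 mg/kg, resume polatuzumab vedotin at the permanently reduced" dose, which is 1.4 mg/kg.

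**Neuropathy, Table 8.51 (section 8.5).** For the same grades, polatuzumab is held until Grade 1 or lower. If that is reached by Day 14, polatuzumab restarts with the next cycle at 1.4 mg/kg. Otherwise: "If not recovered to Grade 1 or lower on or before Day 14, discontinue polatuzumab".

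**General limits.** Section 8.2 permits a delay of 21 days and withdraws patients delayed for more than 3 weeks, apart from exceptional circumstances. The general row of Table 8.32 says: "If study treatment is withheld for 21 days because of a toxicity that is attributable to study treatment, permanently discontinue study treatment".

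**Hematologic toxicity, Table 8.31 (section 8.3).** "Resume venetoclax and polatuzumab vedotin at one level dose reduction after interruption for 2nd occurrence", once the toxicity has resolved. The same item adds "Refer to table 8.21 for dose reduction steps". Table 8.21 is titled for venetoclax and lists only venetoclax doses. Table 8.31 also caps reductions in venetoclax and polatuzumab at 2 levels during induction.

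**The concern.** Both neuropathy rows tell the site what to do with polatuzumab for the same event at the same grades. A patient who recovers after the shorter limit but inside the longer one gets one instruction to resume and one to stop for good, and a site cannot obey both. Two sites could therefore treat the same patient in opposite ways, each relying on protocol text.

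This is a dosing rule for a neurotoxic drug, and sites are likely to need it. Section 1.231 reports that neuropathies were the adverse events that most often led to polatuzumab discontinuation in two earlier studies, and section 10.52 has peripheral sensory neuropathy graded at every evaluation. What is at stake for an affected patient is every remaining polatuzumab dose.

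**Working it through.** No figure in the plan depends on this point, so the check is a comparison of rules and a count of days.

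**1. Is one table ranked above the other?** Section 8.0 introduces the tables without an order. The discretion it gives investigators is for additional dose reductions, not for choosing between resuming and stopping. No other text settles it.

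**2. Do the limits have a start?** Table 8.51 does not say what Day 14 is counted from. Its only day anchor, a footnote about severity on Day 1 of a cycle, is attached to the neutropenia and thrombocytopenia rows. The 21 days in Table 8.32 also have no written start, although counting from the held dose is the natural reading of a delay.

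**3. Width if both limits run from the held Day 1 dose (assumption).** Let d be the day of recovery.
- Table 8.51 stops polatuzumab when d > 14.
- Table 8.32, neuropathy row, resumes when d ≤ 21. The opposed days are 15 to 21: 21 − 14 = 7 days.
- If the general row of Table 8.32 already ends treatment on day 21, resumption needs d < 21. The opposed days are 15 to 20: 20 − 14 = 6 days.

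The neuropathy row and the more-than-3-weeks wording of section 8.2 favor 7. The general row favors 6.

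**4. Sensitivity to the start.** Suppose neuropathy begins h days before the held dose, and day 21 still allows resumption.
- Day 14 from onset, 21 days from the held dose: 21 − (14 − h) = 7 + h days.
- Day 14 from the held dose, 21 days from onset: (21 − h) − 14 = 7 − h days. The limits coincide at h = 7.
- Day 14 as a day of the cycle in which neuropathy begins on day o: the time to recover under Table 8.51 is 14 − o days, so 13 for onset on day 1, 4 for day 10 and 0 for day 14. I give no width here, because a footnote to Table 8.32 intervenes: "Toxicities that occur during the cycle and subside prior to the next cycle should not trigger the suggested dose modifications".

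**5. Dose at stake for one affected patient.** Section 7.2 plans 6 × 1.8 = 10.8 mg/kg. Each dose resumed under Table 8.32 is 1.4 mg/kg, and 1.4 / 10.8 = 13.0% of plan. Section 3.29d excludes neuropathy above Grade 1 at entry, so the earliest dose held for on-study neuropathy is cycle 2. Between 1 and 5 doses can then remain: 13.0% to 5 × 1.4 / 10.8 = 64.8%.

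**6. Design figures.** An exact binomial calculation for the design in section 16.2 (stop at 3 or fewer of 16, success at 11 or more of 46) gives 0.0486 at a true rate of 0.15 and 0.8506 at 0.35. Early-stopping probabilities are 0.790 and 0.134. These match the table in section 16.24 (0.049, 0.851, 0.790, 0.134), and none uses a dosing rule.

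**7. The hematologic cross-reference.** Table 8.31 sends the site to Table 8.21 for a one-level polatuzumab step, and no such step is listed there. The only reduced polatuzumab dose in the protocol is 1.4 mg/kg, in the neuropathy rows: (1.8 − 1.4) / 1.8 = a 22.2% reduction. One listed lower dose does not obviously fit a cap of 2 reductions, and the text does not say whether the cap is per drug or combined.

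**The case against.** The best defense is that section 8.5 is the polatuzumab section and Table 8.32 manages the whole regimen, so a site would follow Table 8.51. That is a sensible default, but it is not written down, and the Table 8.32 row gives its own polatuzumab instruction with its own dose. A second defense, that 21 days is only a maximum delay within which a stricter neuropathy limit can sit, is right for section 8.2 and the general row of Table 8.32. I do not count those as part of the conflict. It does not explain the neuropathy row, which orders resumption.

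Several limits stand. The width rests on an assumed start. Both tables hold polatuzumab at Grade 2-3, require Grade 1 and resume at 1.4 mg/kg. The drug is not given in maintenance. The hematologic gap is narrow: toxicities that subside before the next cycle are exempt, the count rows of Table 8.51 resume without further reduction if counts recover by Day 7, and 1.4 mg/kg is the natural reading of one level down.

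A reader might also infer more than the documents support:
- *That Table 8.32 would keep treating a patient who is already at 1.4 mg/kg.* The cell is broken in the text read from the PDF: the polatuzumab item ends on a semicolon and a fragment of it reappears in the next row. Missing words there prove nothing. Table 8.51 in any case supplies the rule: "If a prior dose reduction to 1.4 mg/kg has occurred, discontinue polatuzumab". Silence in one table beside a rule in the other is not a contradiction.
- *That patients would be dosed during active Grade 2-3 neuropathy.* Neither table allows it.
- *That the 33%-41% discontinuation in section 1.231 measures how many are affected.* It covers any adverse event, in earlier studies that used doses up to 2.4 mg/kg.

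**Conclusion.** The neuropathy rules contradict each other as written, and the sponsor should reconcile them. With both limits counted from the held Day 1 dose, recovery on days 15 to 20, or 15 to 21, brings opposite instructions: 6 or 7 days. Another starting point changes that width. The contradiction in the wording does not depend on it, because both rows are legible and neither is given precedence. How many patients would fall in the gap cannot be taken from the documents.

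The matter is safety and uniform treatment across sites. A reader might infer a threat to the primary analysis, but nothing in the documents shows an effect on the complete response rate, and the significance level, power and 46 evaluable patients stand. The Table 8.31 reference is a secondary clean-up.

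**What to change.** Put one recovery limit, with its starting point, in the neuropathy rows of both Table 8.32 and Table 8.51. The more conservative choice is 14 days from the scheduled Day 1 dose, declared as an exception to the general 21-day maximum delay. A 21-day limit with a stated start would also end the conflict, provided the text says whether day 21 itself still allows resumption. The choice is clinical.

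In Tables 8.21 and 8.31, state the polatuzumab step as 1.8 to 1.4 mg/kg. The sponsor should then reconcile that single step with the cap of 2 reductions and say whether the cap is per drug or combined. I would not write in a stop after 1.4 mg/kg for hematologic toxicity as if it were an edit: it would be a new rule in place of what Table 8.31 allows.

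The cost is an amendment to the text of four tables. With 14 days, patients who recover between 14 and 21 days would stop polatuzumab, so this is a dosing decision as well as an edit. The statistical design needs no change.
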